Patients who turn 18 years of age while participating in this study will be re-consented either in clinic at a routine visit or over the phone. If a participant is re-consented over the phone, a member of the research team

will first mail the "Letter to Reconsent Enrolled Participants" and a blank Consent/HIPAA form to the participant's address listed in the participant's medical record. A member of the research team will call the participant to complete the informed consent discussion over the phone. Once the participant signs the Consent/HIPAA form, he/she will mail it back to the research team member who completed the discussion and he/she will complete the corresponding signature portion. A completed copy will be mailed to the participant and a copy will be uploaded into the participant's medical record. The researcher will document this process on the informed consent discussion form which will be filed with consent form.

O. PROCEDURES TO BE EMPLOYED IN ANALYZING DATA AND THE ANTICIPATED SIGNIFICANCE OF THE PROPOSED STUDY

Data Management and Analysis The data gathered will be entered into RedCap data system with each ID having a unique identifier for each participant. REDCap is a secure, web-based application for building and managing online databases. All data will be de-identified, and samples will only have a unique identifier that will link the unique identifier with the patient's name.

Missing Data: Every effort will be made to avoid missing data. Using logistic regression, the pattern of missing data will be explored. Assuming the data are missing at random (MAR) multiple imputations for items will be used.

Randomization: we will randomize using Piantadosi randomization in blocks of 10. The sample size in this pilot study is small and it would likely result in bad imbalance of the two groups.

Data analysis overview: Summary statistics, such as mean, median, standard deviation, range and correlation will be used as a first step to examine data. To satisfy parametric assumptions, we may perform transformations with justifications if possible and otherwise use non-parametric tests. Statistical software employed for data analysis will be: Cytel StatXact, SAS version 9.4, SPSS Version 24. The power calculation was made using PASS 15.

Heart Rate Variability

The RR-interval time series recorded by the monitor will be detected from surface ECG signals at a sample rate of 1000 Hz and will be downloaded from the devices for further processing using custom HRV analysis software. The heart rate time series will be manually reviewed and processed in segments, excluding those from variability analysis in which artefacts or gaps account for > 15% of the recording. Shorter gaps will be replaced with intervals interpolated from adjacent normal beats. Frequency-domain analysis will be performed after constructing a detrended instantaneous RR-interval time series resampled at 5 Hz by piecewise cubic Hermite interpolation. The absolute and log-transformed power spectrum densities of consecutive segments will be computed for the frequency ranges of 0.04 to 0.15 Hz, designated as low-frequency power (LF), and 0.15 to 0.4 Hz, designated as high-frequency (HF) power. HF fraction will be computed as HF / (LF + HF) in addition to the LF/HF ratio. The HF power has been shown to result predominantly from parasympathetic modulation of heart rate. Time domain HRV parameters will include the standard deviation of all normal sinus beat (NN) intervals and the square root of the mean of the sum of the squares of differences between adjacent NN intervals. In addition to the inspection of the detected RR-intervals provided by the monitor, we will scan the recordings for non-stationary conditions employing Kalman-filter and wavelet-based spectrograms. Statistical analysis will be based on standard parametric or non-parametric group comparisons, as well as correlation computations were appropriate. The agreement between detected beats and the computed parameters for timedomain and frequency-domain HRV analysis between the monitors will be examined using Bland-Altman plots and summarizing using canonical correlations.

P. FINANCIAL RELATIONSHIPS

This study is supported by the 2020 CTSI Traditional Pilot Award. Participants will receive a total stipend of \$70 for participating in this study via check (\$20 after visits 1,2 and \$30 after final visit).

Q. ADVERTISEMENTS / FLIERS

We will not use advertisements or flyers for this protocol.

R. BIBLIOGRAPHY

- 1. Hoekman, D.R., et al., *The Placebo Response in Pediatric Abdominal Pain-Related Functional Gastrointestinal Disorders: A Systematic Review and Meta-Analysis.* J Pediatr, 2017. **182**: p. 155-163.e7.

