Document Date: January 17, 2022

Protocol ID: 1473783

NCT Number: 04247100

PRINCIPAL INVESTIGATOR: [name]

STUDY TITLE: A pilot study of a randomized sham-control auricular TENS unit stimulation to improve symptoms through vagal modulation in pediatric functional gastrointestinal disorders

STUDY PROTOCOL and STATISTICAL ANALYSIS PLAN

A. PURPOSE OF THE STUDY

The main innovation of this application is to begin to unravel a mechanism of action of vagal auricular stimulation. The known facts are that this type of stimulation improves symptoms significantly in FGID, and that it increases vagal cardio-modulation in this context. We know separately that the vagus has strong antiinflammatory effects. However, we do not know if (a) it does so in patients with FGID and (b) if this is a potential mechanism of action for the observed benefit. This project will answer these last 2 questions, and do so in a rigorous way, since placebo effect in FGID is high¹. It is critical to include a sham (tactile sensory) arm in a blinded study context.

Positive results from this study would move the FGID field forward significantly. Potential conclusions would include that (1) the vagal stimulator inhibits the neuroinflammatory cascade, (2) if the degree of inhibition correlates highly with clinical benefit, that this is a potential mechanism for the benefit it proffers; and (3) that neuro-inflammation plays a major role in pediatric FGID, a currently open question.

B. HYPOTHESIS / SPECIFIC AIMS

The overarching hypothesis of this proposal is that auricular vagal micro-stimulation reduces pain through a vagal anti-inflammatory mechanism. The 2 aims of this proposal are (1) to confirm the known cardiovagal modulatory rise and show that clinical improvement correlates with the magnitude of this rise and (2) to determine whether stimulation reduces microinflammatory indices. Comparing 4 weeks of auricular micro-stimulation with sham we will determine whether:

- Aim 1: Cardiovagal modulation (as reflected in high frequency heart rate variability, hfHRV) increases, and correlates with clinical improvement (as reflected in the Functional Disability Inventory (FDI) and a 10 point-liker scale of the 5 worse symptoms (e.g.: abdominal pain, nausea, fatigue, headaches and generalized aches)
- **Objective 1:** To determine if the auricular microstimulator produces the expected increase in hfHRV and determine if this rise parallels evidence of clinical improvement.

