D. DESIGN AND METHODS

We will enroll 30 subjects in this double-blind sham control study. Fifteen subjects will undergo sham stimulation for 4 weeks while the other 15 will have auricular microstimulation for 8 weeks. Then, the 15 subjects who were in the sham group will undergo stimulation for 4 weeks.

We will measure vagal modulation supine and standing utilizing heart rate variability, measure cytokines and mitochondrial bioenergetics through a Seahorse analysis at week 0, 4 and 8.

Inclusion Criteria:

- Female patients 12 18 years old with chronic idiopathic nausea, functional abdominal pain, dyspepsia and/or irritable bowel syndrome.
- English speaking

Exclusion Criteria:

- Patients who are unable to stand upright during the heart rate variability recording
- Patients with a known bleeding disorder
- Patients with swollen, infected, inflamed, or other skin eruptions on outer ear
- Patients with epilepsy
- Patients with any implanted cardiac pacemaker or defibrillator
- Patients with serious arterial circulatory problems in the lower limbs
- Patients with abdominal or inguinal hernia

- Patients who are pregnant
- Any unstable medical condition, such as renal disease, uncontrolled diabetes, etc.
- Requires new medication during the 8 weeks of the study that may affect the gastrointestinal symptoms, vagal modulation or immune response.
- Inability to answer questionnaires or report pain in a 0-10 visual analog scale.

Week 0 – Visit 1 (Enrollment)

A member of the research team will approach the patient and his/her legal guardian during his/her visit to the Functional and Gastrointestinal Disorders Clinic. If the patient and his/her guardian are unable to complete consent documents during the visit, the researcher may collect consent over the phone or at the study baseline visit in the Pediatric Translational Research Unit (TRU), prior to starting study procedures.

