A qualified nurse from the Pediatric Translational Research Unit will collect up to 59ccs (3-4 tablespoons) of blood from each participant at study visit weeks 0, 4, and 8. A member of the research team who has completed laboratory training on the use of the centrifuge and hood, will initially process the blood prior to escorting the sample to [name] lab in coded tubes. Members of [name] lab will not be privy to any PHI. Due to decreased laboratory staffing/resources during Covid-19, samples will be frozen by a member of the research team after initial processing. These samples will remain viable until flow cytometry can be completed can be

	Week 0 Visit	Week 4 Visit	Week 8 Visit
Consent	Х		
Pregnancy Test	Х		
Device Randomization	Х	X	Х
MD Assessment	X	X	
TENS Unit and Auricular Clip Placement	Х	Х	Х
HRV	Х	Х	Х
FDI (Child and Adolescent Form and Parent Form)	Х	Х	Х
Symptom Intensity Questionnaire	Х	X	X
PCS-C	Х	X	X
RCADS	Х	X	
TENS Unit Daily Recording Diary	Х	X	X
Cytokines and Flow Cytometry			

completed by [name] lab. Primary blood mononuclearcells will be isolated by density-gradient centrifugation through Ficol/Hypaque (Pharmacia), suspended (8 ′ 106cellsml-1) in RPMI 1640 medium with 10% heat inactivated human serum (Gemini Bio-Products), and seeded in flasks. After incubation for 2h at 378C, adherent cells will be detached with 10mM EDTA, resuspended (106 cellsml-1) in medium supplemented with human MCSF (Sigma; 2 ngml-1), and seeded onto 24-well tissue culture plates (106cellsper well). Cells will be allowed to differentiate for seven days in the presence of MCSF. On day seven, fresh medium without MCSF will be added. LPS will be added to the cultures at a final concentration of 100ngml-1. Supernatants will be collected 4 and 20h after the addition of LPS and prepared for cytokine analysis. We will ship samples to Eve Technologies (located in Canada) where they will use their assay service to analyze the human cytokine array/Chemokine 42-Plex. We will use the high sensitivity assay due to low levels of cytokines in humans and will evaluate a panel consisting of EGF, Eotaxin-1, FGF-2, Flt-3L, Fractalkine, G-CSF, GM-CSF, GRO(alpha), IFNalpha2, IFNgamma, IL-1alpha, IL-1 beta, IL-1ra, IL-2, IL-3, IL-4, IL-5, IL-6, IL-7, IL-8, IL-9, IL-10, IL-12 (p40), IL-12 (p70), IL-13, IL-15, IL-17A, IL-18, IP-10, MCP-1, MCP-3, MDC, MIP-1alpha, MIP-1beta, PDGF-AA, PDGF-AB/BB, RANTES, sCD40L, TGFalpha, TNFalpha, TNFbeta, VEGF-A.

Pregnancy Test

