If this auricular TENS unit device produces the expected results, it will: 1) provide a portable, affordable tool to decrease symptoms in FGID; 2) corroborate that increasing vagal modulation improves symptoms in FGID; and 3) if the pro-inflammatory cytokines decrease and mitochondrial bioenergetics increases, it will support the role of the vagus as an anti-inflammatory function in FGID and will expand the current understanding of the action of the vagus on the cardiac mitochondria to also the mitochondria in the blood cells.

L. STOPPING POINTS THAT WOULD NOT ALLOW THE STUDY TO CONTINUE AS PROPOSED

The stopping points for the study include the request to stop by the patient or parent/guardian as well as the inability to recruit participants or unexpected adverse events that might result in stopping the study.

M. IS THERE A DATA SAFETY MONITORING BOARD IN PLACE? WHO ARE IT'S MEMBERS? HOW OFTEN DO THEY MEET?

We will not use a DSMB for this project.

N. DESCRIBE HOW THE CONSENT AND ASSENT PROCESS WILL TAKE PLACE. INCLUDE A LIST OF APPROPRIATELY TRAINED PERSONNEL WHO WILL BE INVOLVED.

Written informed consent for participation will be obtained from parents for their child's participation. Written assent will be obtained from youth 12-13 years of age using the CHW assent form. Adolescents ages 14 and up will sign the assent line on consent form per CHW policy. Participants aged 18 years will sign the adult portion on the consent form. The study will be introduced to participants at the CHW GI clinic following their standard of care visit. Consent will be obtained by a study investigator or a member of the research team at the participant's visit to the CHW GI clinic, or at the baseline visit at the TRU prior to any study procedures. Participants will have the option of having the consent/assent document read aloud to them to facilitate understanding. Copies of signed consent/assent documents will be given to participants.

Although the MD Assessment form includes questions regarding whether the participant's various family members have been diagnosed with migraine, fibromyalgia, irritable bowel syndrome or if they are double jointed, we do not believe these various family members to be secondary subjects. The goal of collecting this information is to determine factors that may contribute to the subject responding or not to the microstimulation. For this protocol, we will only consent the child participant.

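### A cytokine fall in cultured blood-derived cells, active versus sham within FGID, cannot show that neuro-inflammation plays a major role in FGID; Section A's potential conclusions should be narrowed

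*Combined protocol and SAP*

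**What the plan says.** Section A (Purpose of the study) sets out what positive results might establish. It opens with "Potential conclusions would include that (1) the vagal stimulator inhibits the neuroinflammatory cascade". The second item is conditional: "if the degree of inhibition correlates highly with clinical benefit, that this is a potential mechanism for the benefit it proffers". The third, "that neuro-inflammation plays a major role in pediatric FGID, a currently open question", carries no condition of its own.

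Section D restricts entry to female patients "with chronic idiopathic nausea, functional abdominal pain, dyspepsia and/or irritable bowel syndrome". It plans 30 participants, 15 per arm. One arm has sham for 4 weeks and then active stimulation for 4 weeks; the other has active stimulation for all 8.

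Aim 2 in Section B takes LPS-induced cytokine production as the inflammatory measure. Section F gives the method: adherent blood mononuclear cells are cultured ("Cells will be allowed to differentiate for seven days in the presence of MCSF"), LPS is added, and supernatants are collected at 4 and 20 hours.

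Aim 1 plans to relate the rise in hfHRV to clinical improvement. Aim 2 states no corresponding analysis for cytokines. Section O offers summary statistics including correlation and, under the heart rate variability heading, group comparisons and correlations. It describes no model that relates cytokine change to clinical change.

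**The concern.** The third conclusion concerns the cause of the disease, while the trial tests what a device does. These are different questions, and a clear answer to the second leaves the first open. The first conclusion has a milder form of the same problem, because it names a neuro-inflammatory cascade where the assay reads a peripheral cell response outside the body. The second depends on a correlation whose analysis is not defined, and the simplest way of computing it would be partly driven by the treatment effect itself.

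At stake is what a positive pilot could be taken to show. The data would be the same, but a reader of Section A could credit them with settling a disease-mechanism question that the trial does not test.

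**Working it through.** The plan gives no figure for this point, so the check compares each conclusion with the design and then works through one illustration.

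**Conclusion (3) against the design**

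- *Population (Section D).* All participants have an FGID. No non-FGID group or reference range is planned, so the trial cannot show whether the measured cytokine response is abnormal in FGID.
- *Contrast (Sections B and D).* Active versus sham is randomized up to week 4; after that both arms receive active stimulation. The contrast estimates the effect of stimulation on the assay.
- *Assay (Section F).* It measures LPS-induced release by blood-derived cells after seven days in culture. The other biological measures in Section D and Section F are heart rate variability, blood flow cytometry and mitochondrial bioenergetics. None directly measures inflammation in the nervous system or the gut.
- *What a fall would mean.* Section A takes it as known that the vagus has strong anti-inflammatory effects. Section C reports that a cervical vagal stimulator lowered TNF-alpha production. On those premises a cytokine fall is expected whether or not inflammation drives FGID. The fall would address Section A's narrower question, whether the vagal effect occurs in patients with FGID, at the level of this assay. By itself it would not address the role of inflammation in the disease.

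**Conclusion (2): what a pooled correlation would contain**

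Assumptions for illustration: two equal arms; cytokine change and clinical change each scaled to a within-arm SD of 1 and signed so that improvement is positive; a mean difference of d SD between arms on each; no association within arm.

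- Each arm mean lies d/2 from the overall mean, so the pooled covariance is 0 + d²/4.
- The pooled variance of each outcome is 1 + d²/4.
- Pooled r = (d²/4) / (1 + d²/4).

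| d (SD) | d²/4 | pooled r |
|---|---|---|
| 1.06 | 0.281 | 0.281/1.281 = 0.22 |
| 1.5 | 0.5625 | 0.5625/1.5625 = 0.36 |
| 2 | 1 | 1/2 = 0.50 |

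The value 1.06 is the standardized difference that 15 per arm detects with 80% power in a two-sided 5% t-test. It is not an effect stated in the plan, which gives no SD. With 30 participants, an r of about 0.36 is the two-sided 5% critical value, so the middle row alone would sit at nominal significance. Including arm in the model removes this between-arm component.

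**How far a high correlation would go**

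By Fisher's z with n = 30, an observed r of 0.7 gives 0.867 ± 1.96/√27, that is 0.490 to 1.245, or a 95% interval for r of 0.45 to 0.85. Shared variance would then lie between about 21% and 72%. Even this favourable result leaves open whether any role is major, and a correlation between two changes measured after randomization is not in itself causal.

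**The case against.** The strongest reply is that Section A commits the trial to little. It speaks of potential conclusions in a pilot. The third is not an aim, an endpoint or a test, and Aim 2 is already worded at the level of the assay. Section K is also narrower, referring to the vagus as anti-inflammatory in FGID. All of this stands. It makes the point one of wording and analysis choice, and it shows that the better wording is already in the document. It does not give the third item the condition it lacks.

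Four stronger readings are tempting, and the documents do not support them.

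- *The trial would yield no evidence at all on inflammation in FGID.* A randomized cytokine fall together with clinical benefit that tracked it within arm would be indirect evidence. It would also have some value without a healthy comparison group, whose absence is not decisive on its own.
- *The plan will pool the correlation across arms.* No section says so. The plan leaves the analysis undefined, and the shifts in the table are assumed. The resulting values are modest, while the second conclusion asks for a high correlation (with no threshold given) and claims only a potential mechanism.
- *A positive trial will be reported as settling the disease question.* The plan has no reporting rule to that effect.
- *Section K relies on a bioenergetics measure that the plan never provides for.* Section D names a Seahorse analysis at weeks 0, 4 and 8. What is missing is procedural and analysis detail, which is a separate matter.

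It can also be argued that blood-cell cytokine release is a fair proxy, since Section C links the neuro-inflammatory cascade to low-grade systemic inflammation. That depends on sources outside the documents. It would not establish a major role in any case.

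**Conclusion.** The concern holds in limited form. The third potential conclusion does not follow from the design, and the neuro-inflammatory wording of the first goes beyond the assay. The second needs an analysis that separates association within arm from the effect of treatment on both outcomes. These judgements rest on the population, contrast and assay as written, and need no assumed numbers. The pooled correlations of 0.22 to 0.50 illustrate why arm belongs in the model; they depend on the assumed equal, independent shifts and do not predict this trial's result.

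The consequence is small. Randomization, visits, endpoints and sample size are unaffected. What changes is what a positive result may be said to show.

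**What to change.** 1. In Section A, delete conclusion (3), or recast it as a hypothesis for a later study.
2. Restate conclusion (1) to match Aim 2: stimulation lowers LPS-induced cytokine production by blood-derived cells relative to sham.
3. In Section O, base conclusion (2) on a regression of week-4 clinical change on week-4 cytokine change with randomized arm as a covariate. Report the cytokine coefficient with its confidence interval and label the analysis hypothesis-generating. Week 4 is the right time because both arms are on active stimulation afterwards.

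The cost is narrower claims and one degree of freedom: with 30 complete cases, residual degrees of freedom fall from 28 to 27. No extra data are needed. The arm term removes the artefact described above, but it does not make the cytokine coefficient causal, since other factors may drive both changes within an arm.
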